#### **Attribution of Toxicity:**

When study interventions are administered in combination, attribution of an adverse event to a single component is likely to be difficult. Therefore, while the investigator may attribute a toxicity event to the assigned treatment combination, to pralatrexate alone (Arm A or B), to decitabine alone (Arm B or C) or to pembrolizumab alone, for adverse events listed in Table 10, both (all, for Arm B) interventions must be held according to the criteria in Table 10 Dose Modification and Toxicity Management Guidelines for Immune-Related Adverse Events.

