#### **Holding Study Interventions:**

When study interventions are administered in combination, if the AE is considered immune-related, both (all for Arm B) interventions should be held according to recommended dose modifications.

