Pneumonitis	Grade 2	Withhold	
 
• Administer corticosteroids (initial dose of 1-2 mg/kg prednisone or equivalent) followed by taper
 
• Add prophylactic antibiotics for opportunistic infections
 
	
 
• Monitor participants for signs and symptoms of pneumonitis
 
• Evaluate participants with suspected pneumonitis with radiographic imaging and initiate corticosteroid treatment
 

	Grade 3 or 4, or recurrent Grade 2	Permanently discontinue		
Diarrhea / Colitis	Grade 2 or 3	Withhold	
 
• Administer corticosteroids (initial dose of 1-2 mg/kg prednisone or equivalent) followed by taper
 
	
 
• Monitor participants for signs and symptoms of enterocolitis (ie, diarrhea, abdominal pain, blood or mucus in stool with or without fever) and of bowel perforation (ie, peritoneal signs and ileus).
 
• Participants with <math>\geq</math> Grade 2 diarrhea suspecting colitis should consider GI consultation and performing endoscopy to rule out colitis.
 
• Participants with diarrhea/colitis should be advised to drink liberal quantities of clear fluids. If sufficient oral fluid intake is not feasible, fluid and electrolytes should be substituted via IV infusion.
 

	Recurrent Grade 3, or Grade 4	Permanently discontinue		
AST / ALT elevation or Increased	Grade 2 a	Withhold	
 
• Administer corticosteroids (initial dose of
 
	
 
• Monitor with liver function tests (consider weekly or more frequently until liver enzyme
 

bilirubin			0.5- 1 mg/kg prednisone or equivalent) followed by taper	value returned to baseline or is stable
	Grade 3 b or 4 c	Permanently discontinue	
 
Administer corticosteroids (initial dose of 1-2 mg/kg prednisone or equivalent) followed by taper
 
	

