### 7.3.2 Pralatrexate

Patient treated with pralatrexate are at risk of developing mucositis. The risk of developing mucositis can be lowered by pretreating patient with leucovorin 15 mg PO BID that has to be held the day before, day of and day after pralatrexate administration. The treatment with leucovorin will be given with treatment as noted above but can be given at the treating physician's discretion for pralatrexate related mucositis (i.e. in schedule delays). Pralatrexate and decitabine can induce hematologic toxicity that should be address with Neupogen/Neulasta support at the treating physician's discretion and as suggested in Table 12 and Table 13.

Doses may be omitted or reduced based on patient tolerance. Omitted doses will not be made up for at the end of the cycle; once a dose reduction occurs for toxicity, there will be no re-escalation. For dose modifications and omissions, use the suggested guidelines in Table 11, Table 12 and Table 13 below.

Table 11: Suggested Guidelines for Pralatrexate Dose Modifications for Mucositis after Cycle 1

Mucositis Grade a on the Day of Treatment	Action	Dose upon recovery to Grade ≤ 1
Grade 2	Omit dose	Maintain dose level
Grade 2 recurrence	Omit dose	Reduce to one dose level below
Grade 3	Omit dose	Reduce to one dose level below
Grade 4	Stop therapy	No further treatment with pralatrexate

a Per NCI CTCAE, Version 3.0

Table 12: Suggested Guidelines for Pralatrexate Dose Modifications for Hematologic Toxicities

Blood Counts on the Day of Treatment	Duration of Toxicity	Action	Dose upon re-start
Platelets < 50,000/µL	1 week	Omit dose	Continue prior dose
	2 weeks	Omit dose	Reduce to one dose level below
	>2 weeks	Stop therapy	No further pralatrexate
ANC 500-1,000/µL and no fever	1 week	Omit dose	Continue prior dose
ANC 500-1,000/µL with fever (a single temperature of > 38.3°C or sustained temperature of ≥ 38°C for over one hour) or ANC <500/µL	1 week	Omit dose, give G-CSF or GM-CSF	Continue prior dose with G-CSF or GM-CSF support
	2 weeks or recurrence	Omit dose, give G-CSF or GM-CSF	Reduce to one dose level below with G-CSF or GM-CSF support
	>2 weeks or 2nd recurrence	Stop therapy	No further pralatrexate

Table 13: Suggested Guidelines for Pralatrexate Dose Modifications for All Other Treatment Related Toxicities

Toxicity Grade a on the Day of Treatment	Action	Dose upon recovery to Grade ≤ 2
Grade 3	Omit dose	Reduce to one dose level below

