- **Hepatotoxicity:** Liver function test abnormalities have been observed with pralatrexate use. Persistent abnormalities may indicate hepatotoxicity and may require dosage modification as indicated in table 13 and in the FDA package insert.

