## 7.8.2 Supportive Care Guidelines for Immune-related AEs

Subjects should receive appropriate supportive care measures as deemed necessary by the treating investigator. Suggested supportive care measures for the management of adverse events with potential immunologic etiology are outlined below. Where appropriate, these guidelines include the use of oral or intravenous treatment with corticosteroids as well as additional anti-inflammatory agents if symptoms do not improve with administration of corticosteroids. Note that several courses of steroid tapering may be necessary as symptoms may worsen when the steroid dose is decreased. For each disorder, attempts should be made to rule out other causes such as metastatic disease or bacterial or viral infection, which might require additional supportive care. The treatment guidelines are intended to be applied when the investigator determines the events to be related to pembrolizumab (see section 7.3.1).

Note: if after the evaluation the event is determined not to be related, the investigator does not need to follow the treatment guidance (as outlined below). Refer to Section 5.0 and 7.0 for dose modification, escalation and de-escalation rules.

It may be necessary to perform conditional procedures such as bronchoscopy, endoscopy, or skin photography as part of evaluation of the event.

- **Pneumonitis:**
  - **Grade 2 events** withhold treatment and treat with systemic corticosteroids. When symptoms improve to Grade 1 or less, steroid taper should be started and continued over no less than 4 weeks.
  - For **Grade 3-4 events and recurrent grade 2**, immediately treat with intravenous steroids. Permanently discontinue treatment. Administer additional anti-inflammatory measures, as needed.
  - Add prophylactic antibiotics for opportunistic infections in the case of prolonged steroid administration.
- **Diarrhea/Colitis:**

Subjects should be carefully monitored for signs and symptoms of enterocolitis (such as diarrhea, abdominal pain, blood or mucus in stool, with or without fever) and of bowel perforation (such as peritoneal signs and ileus).

  - All subjects who experience diarrhea/colitis should be advised to drink liberal quantities of clear fluids. If sufficient oral fluid intake is not feasible, fluid and electrolytes should be substituted via IV infusion. For Grade 2 or higher diarrhea, consider GI consultation and endoscopy to confirm or rule out colitis.

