    - Treat with an initial dose of IV corticosteroid followed by oral corticosteroids. Withhold or permanently discontinue treatment, at discretion of the investigator or treating physician. When symptoms improve to Grade 1 or less, steroid taper should be started and continued over no less than 4 weeks.
- **Hepatic:**
  - For **Grade 2** events, monitor liver function tests more frequently until returned to baseline values (consider weekly).
    - Treat with IV or oral corticosteroids
  - For **Grade 3-4** events, treat with intravenous corticosteroids for 24 to 48 hours. Permanently discontinue treatment for grade 4 or grade 3 toxicity.
  - When symptoms improve to Grade 1 or less, a steroid taper should be started and continued over no less than 4 weeks.
- **Renal Failure or Nephritis:**
  - For **Grade 2** events, withhold treatment and treat with corticosteroids.
  - For **Grade 3-4** events, treat with systemic corticosteroids. Permanently discontinue treatment.
  - When symptoms improve to Grade 1 or less, steroid taper should be started and continued over no less than 4 weeks
- For other immune related adverse events (IRAE) including myocarditis, encephalitis and Gullian-Barre and further clarification of the above mention IRAE refer to table 10 and section 7.3.1**Management of Infusion Reactions:** Signs and symptoms usually develop during or shortly after drug infusion and generally resolve completely within 24 hours of completion of infusion.

Treatment guidelines for subjects who experience an infusion reaction associated with administration of pembrolizumab are in Table 14 below.

Table 14: Infusion Reaction Treatment Guidelines

NCI CTCAE Grade	Treatment	Premedication at subsequent dosing
Grade 1 Mild reaction; infusion interruption not indicated; intervention not indicated	Increase monitoring of vital signs as medically indicated until the subject is deemed medically stable in the opinion of the investigator.	None
Grade 2 Requires infusion	Stop Infusion and monitor symptoms.	Subject may be premedicated 1.5h ( $\pm$ 30 minutes) prior to infusion of

NCI CTCAE Grade	Treatment	Premedication at subsequent dosing

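### Sections 7.3.1, 7.8.1 and 7.8.2 set different triggers, so in Arms A and B a Grade 3 AST/ALT rise attributed to pralatrexate can either end all treatment or only lower the pralatrexate level

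*Protocol*

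**What the plan says.** Five places in the protocol bear on the same event.

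- **Section 7.3.1, Attribution of Toxicity.** The investigator may attribute an event to the combination, "to pralatrexate alone (Arm A or B), to decitabine alone (Arm B or C) or to pembrolizumab alone". Even so, "for adverse events listed in Table 10, both (all, for Arm B) interventions must be held according to the criteria in Table 10".
- **Section 7.3.1, Holding Study Interventions.** The very next paragraph adds a condition: "if the AE is considered immune-related, both (all for Arm B) interventions should be held according to recommended dose modifications". A note under Table 10 likewise leaves events that are not immune-related to clinical practice.
- **Table 10.** The row that begins "AST / ALT elevation or Increased" (it continues with bilirubin) gives withhold at Grade 2 and permanent discontinuation at Grade 3 or 4. The column is headed as the action with pembrolizumab.
- **Section 7.8.2.** "The treatment guidelines are intended to be applied when the investigator determines the events to be related to pembrolizumab"; if the event is judged unrelated, the investigator is released from the treatment guidance. Its hepatic entry for Grade 3-4 reads "Permanently discontinue treatment for grade 4 or grade 3 toxicity".
- **Section 7.8.1 and Table 13.** On pralatrexate liver abnormalities: "Persistent abnormalities may indicate hepatotoxicity and may require dosage modification as indicated in table 13". Table 13 is titled "Suggested Guidelines for Pralatrexate Dose Modifications for All Other Treatment Related Toxicities". At Grade 3 it omits the dose and, on recovery to Grade 2 or less, resumes pralatrexate one level lower. At Grade 4 it ends pralatrexate.

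Section 7.10 adds that once any drug in the assigned combination is discontinued, or has to be held for an adverse event for more than 2 weeks, all study treatment should stop.

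**The concern.** The protocol uses three different tests for when the immune-event rules apply: the event is listed in Table 10, whichever drug is blamed; the event is considered immune-related; or the event is judged related to pembrolizumab. These tests do not coincide. A liver-enzyme rise that the investigator puts down to pralatrexate passes the first and can fail the other two. Section 7.8.1 meanwhile names another table for that toxicity.

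The choice decides whether a participant leaves all study treatment or continues at a lower pralatrexate level. Two sites reading the same protocol could act differently and each cite a section in support. Discontinuations in Arms A and B would then partly reflect which section a site followed.

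**Working it through.** No figure in the protocol is at issue, so the check is to trace one event through the text. Take a Grade 3 AST/ALT rise in Arm A or Arm B that the investigator attributes to pralatrexate alone.

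**Route 1, by listing.**
1. The attribution paragraph of Section 7.3.1 names attribution to pralatrexate alone and still applies the Table 10 criteria to all drugs in the arm.
2. Table 10 lists AST/ALT elevation and gives permanent discontinuation at Grade 3.
3. The column speaks of pembrolizumab only, but under Section 7.10 discontinuing any one drug ends all study treatment.

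Result: the participant is off all study treatment.

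**Route 2, by cause.**
1. The holding paragraph of Section 7.3.1 and the note under Table 10 take the event out of Table 10 if it is not considered immune-related. Section 7.8.2 waives its guidance if the event is not related to pembrolizumab.
2. Section 7.8.1 sends pralatrexate liver abnormalities to Table 13.
3. Table 13 at Grade 3 omits the dose and resumes one level lower on recovery.

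Result: the participant stays on treatment at a lower pralatrexate level.

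**Do the cross-references settle it?** No. Table 10 refers to Section 7.8.2 for detail. Section 7.8.2 refers back to Section 7.3.1 on relatedness, and its note sends dose modification to Sections 5.0 and 7.0. The reader ends at the paragraph where the difficulty began.

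**Does the restart paragraph settle it?** No. Section 7.3.1 gives attribution a role there: when the toxicity is put down to pralatrexate or decitabine alone, restarting pembrolizumab may be considered. That applies only if the Table 10 conditions are met, and the Grade 3 liver row states no condition for resuming. The paragraph also contemplates pembrolizumab continuing alone, which does not fit the note in Section 7.10.

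**Where the routes really part.**
- Grade 4: Table 13 ends pralatrexate and Section 7.10 then ends everything, so both routes stop treatment.
- Grade 3 with slow recovery: Section 7.2 discontinues treatment after an interruption of more than 14 days, so Route 2 also ends there.
- Grade 3 with recovery inside that limit: the outcomes differ as described.
- Grade 2: Table 10 withholds and Table 13 has no row. Section 5.4, however, requires AST/ALT no higher than 2.0 x ULN to start a cycle (3.0 x ULN or baseline with liver involvement). Table 10 Grade 2 is above 3.0 x ULN when baseline is normal, so the next cycle is blocked anyway. Any difference is confined to doses within a cycle.

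**The case against.** The strongest reply is that a coherent reading exists. Section 7.3.1 opens by tying these events to pembrolizumab exposure and asks sites to confirm the cause or exclude others. The table is titled for immune-related events, the holding paragraph repeats that condition, and the note under the table excludes the rest. On this reading the site first decides whether the event is immune-related. If it is, Table 10 governs all drugs; if not, Section 7.8.1 and Table 13 do. Tables 11 to 13 are also only suggested guidelines, and Section 7.8.1 speaks of persistent abnormalities that may need modification.

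This is plausible, and it limits the point to a matter for reconciliation. It does not remove it. The reading leaves little work for the clause that applies Table 10 even when pralatrexate or decitabine alone is blamed. It also does not align the immune-related test with the separate test of relatedness to pembrolizumab in Section 7.8.2.

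A reader might infer more than the documents support:

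- **That the rule reaches days 1 to 7 of cycle 1 in Arms B and C and so distorts the DLT denominators.** The opening of Section 7.3.1 concerns events associated with pembrolizumab exposure, and none has been given by then. The attribution paragraph says nothing about DLT evaluability.
- **That corticosteroids are forced on participants with pralatrexate-attributed events.** The attribution paragraph requires holding. Section 7.8.2 waives the treatment guidance for unrelated events.
- **That ORR moves by a calculable amount.** Under Section 9.1.6.5 a participant with at least one cycle stays evaluable for response, so discontinuation does not by itself change the count.
- **That Arm C has the same clash of tables.** Table 13 concerns pralatrexate, which Arm C does not receive. Only the unclear trigger carries over, for events attributed to decitabine.

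**Conclusion.** The point holds in a bounded form. The protocol states more than one trigger for Table 10 and does not rank them. In Arms A and B, a Grade 3 AST/ALT rise attributed to pralatrexate that recovers within the permitted interruption can end all study treatment or lead to resumption one pralatrexate level lower, with textual support for each.

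The size is qualitative: a different outcome for each such participant. No frequency can be given, because the protocol states no liver-event rate, and no effect on ORR or on the dose-finding model is shown. The conclusion assumes that sites read the attribution paragraph as worded and that Section 7.10 extends a pembrolizumab discontinuation to all drugs. The sections should be reconciled because they govern safety actions that sites must apply consistently. This review takes no view on which clinical rule is right.

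**What to change.** Amend Sections 7.3.1 (attribution, holding and restart paragraphs, and the Table 10 note), 7.3.2 (Table 13), 7.8.1, 7.8.2 and 7.10 so that they agree on two things:

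1. One trigger for Table 10, used in the same words throughout: any listed event, an event considered immune-related, or an event judged related to pembrolizumab.
2. Which table or source governs a listed event attributed to pralatrexate alone or to decitabine alone, and how that fits with the restart paragraph and the Section 7.10 note.

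The sponsor's clinical team decides which rule stands. The cost is a short paragraph in an amendment with matching edits in the sections named. It needs no extra participants, visits or procedures, and no change to the statistical design.

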#### **Holding Study Interventions:**

When study interventions are administered in combination, if the AE is considered immune-related, both (all for Arm B) interventions should be held according to recommended dose modifications.

#### **Restarting Study Interventions:**

Participants may not have any dose modifications (no change in dose or schedule) of pembrolizumab in this study, as described in Table 10.

- If the toxicity does not resolve or the criteria for resuming treatment are not met, the participant must be discontinued from all study interventions.
- If the toxicities do resolve and conditions are aligned with what is defined in Table 10, the assigned treatment combination (based on Arm assignment) may be restarted at the discretion of the investigator. In these cases where the toxicity is attributed to the assigned treatment combination, to only the combination of decitabine and pralatrexate (Arm B only), or to decitabine or pralatrexate alone, re-initiation of pembrolizumab either as a monotherapy or, for Arm B only, combined with decitabine or pralatrexate if the AE is not attributed to one of the drugs, may be considered if the principal investigator's agrees.

Table 10: Dose Modification Guidelines for Immune-Related Adverse Events Associated with Monotherapy and IO Combinations. For further details please see section 7.8.2

General instructions: 
 
1. The Corticosteroid taper should begin when the irAE is <math>\leq</math> Grade 1 and continue at least 4 weeks.
 
2. Study intervention must be permanently discontinued if the irAE does not resolve or the corticosteroid dose is not <math>\leq</math> 10 mg/day within 12 weeks of the last study intervention treatment.
 
3. If study intervention has been withheld, study intervention may resume after the irAE decreased to <math>\leq</math> Grade 1 after corticosteroid taper.
 
4. Severe and life-threatening irAEs should be treated with IV corticosteroids followed by oral steroids. Other immunosuppressive treatment should begin if the irAEs are not controlled by corticosteroids.
 
				
Immune-related AEs	Toxicity grade (CTCAE v5.0)	Action with pembrolizumab	Corticosteroid and/or other therapies	Monitoring and follow-up
Pneumonitis	Grade 2	Withhold	
 
• Administer corticosteroids (initial dose of 1-2 mg/kg prednisone or equivalent) followed by taper
 
• Add prophylactic antibiotics for opportunistic infections
 
	
 
• Monitor participants for signs and symptoms of pneumonitis
 
• Evaluate participants with suspected pneumonitis with radiographic imaging and initiate corticosteroid treatment
 

	Grade 3 or 4, or recurrent Grade 2	Permanently discontinue		
Diarrhea / Colitis	Grade 2 or 3	Withhold	
 
• Administer corticosteroids (initial dose of 1-2 mg/kg prednisone or equivalent) followed by taper
 
	
 
• Monitor participants for signs and symptoms of enterocolitis (ie, diarrhea, abdominal pain, blood or mucus in stool with or without fever) and of bowel perforation (ie, peritoneal signs and ileus).
 
• Participants with <math>\geq</math> Grade 2 diarrhea suspecting colitis should consider GI consultation and performing endoscopy to rule out colitis.
 
• Participants with diarrhea/colitis should be advised to drink liberal quantities of clear fluids. If sufficient oral fluid intake is not feasible, fluid and electrolytes should be substituted via IV infusion.
 

	Recurrent Grade 3, or Grade 4	Permanently discontinue		
AST / ALT elevation or Increased	Grade 2 a	Withhold	
 
• Administer corticosteroids (initial dose of
 
	
 
• Monitor with liver function tests (consider weekly or more frequently until liver enzyme
 

bilirubin			0.5- 1 mg/kg prednisone or equivalent) followed by taper	value returned to baseline or is stable
	Grade 3 b or 4 c	Permanently discontinue	
 
Administer corticosteroids (initial dose of 1-2 mg/kg prednisone or equivalent) followed by taper
 
	
Type 1 diabetes mellitus (T1DM) or Hyperglycemia	New onset T1DM or Grade 3 or 4 hyperglycemia associated with evidence of $\beta$ -cell failure	Withhold d	
 
Initiate insulin replacement therapy for participants with T1DM
 
Administer anti-hyperglycemic in participants with hyperglycemia
 
	
 
Monitor participants for hyperglycemia or other signs and symptoms of diabetes.
 

Hypophysitis	Grade 2	Withhold	
 
Administer corticosteroids and initiate hormonal replacements as clinically indicated.
 
	
 
Monitor for signs and symptoms of hypophysitis's (including hypopituitarism and adrenal insufficiency)
 

	Grade 3 or 4	Withhold or permanently discontinue d		
Hyperthyroidism	Grade 2	Continue	
 
Treat with nonselective beta-blockers (e.g., propranolol) or thionamides as appropriate
 
	
 
Monitor for signs and symptoms of thyroid disorders.
 

	Grade 3 or 4	Withhold or permanently discontinue d		
Hypothyroidism	Grade 2, 3 or 4	Continue	
 
Initiate thyroid replacement hormones (e.g., levothyroxine or liothyronine) per standard of care
 
	
 
Monitor for signs and symptoms of thyroid disorders.
 

Nephritis grading according to increased creatinine or acute kidney injury	Grade 2	Withhold	
 
Administer corticosteroids (prednisone 1-2 mg/kg or equivalent) followed by taper.
 
	
 
Monitor changes of renal function
 
		
	Grade 3 or 4	Permanently discontinue				
Neurological Toxicities	Grade 2	Withhold	
 
Based on severity of AE administer corticosteroids
 
	
 
Ensure adequate evaluation to confirm etiology and/or exclude other causes
 
		
	Grade 3 or 4	Permanently discontinue				
Myocarditis	Grade 1	Withhold	
 
Based on severity of AE administer corticosteroids
 
	
 
Ensure adequate evaluation to confirm etiology and/or exclude other causes
 
		
	Grade 2, 3 or 4	Permanently discontinue				
Exfoliative Dermatological Conditions	Suspected SJS, TEN, or DRESS	Withhold	
 
Based on type and severity of AE administer corticosteroids
 
	
 
Ensure adequate evaluation to confirm etiology and/or exclude other causes
 
		
	Confirmed SJS, TEN, or DRESS	Permanently discontinue				
All other irAEs	Persistent Grade 2	Withhold	
 
Based on type and severity of AE administer corticosteroids
 
	
 
Ensure adequate evaluation to confirm etiology and/or exclude other causes
 
		
	Grade 3	Withhold or discontinue based on the event e				
	Grade 4 or recurrent Grade 3	Permanently discontinue				

AE(s)=adverse event(s); ALT= alanine aminotransferase; AST=aspartate aminotransferase; CTCAE=Common Terminology Criteria for Adverse Events; DRESS=Drug Rash with Eosinophilia and Systemic Symptom; GI=gastrointestinal; IO=immuno-oncology; ir=immune related; IV=intravenous; SJS=Stevens-Johnson Syndrome; T1DM=type 1 diabetes mellitus; TEN=Toxic Epidermal Necrolysis; ULN=upper limit of normal.
						

Note: Non-irAE will be managed as appropriate, following clinical practice recommendations.
						

a AST/ALT: >3.0 to 5.0 x ULN if baseline normal; >3.0 to 5.0 x baseline, if baseline abnormal; bilirubin: >1.5 to 3.0 x ULN if baseline normal; >1.5 to 3.0 x baseline if baseline abnormal
						

b AST/ALT: >5.0 to 20.0 x ULN, if baseline normal; >5.0 to 20.0 x baseline, if baseline abnormal; bilirubin: >3.0 to 10.0 x ULN if baseline normal; >3.0 to 10.0 x ULN if baseline normal; >3.0 to 10.0 x baseline if baseline abnormal
						

c AST/ALT: >20.0 x ULN, if baseline normal; >20.0 x baseline, if baseline abnormal; bilirubin: > 10.0 x ULN if baseline normal; >10.0 x baseline abnormal
						

d The decision to withhold or permanently discontinue pembrolizumab is at the discretion of the investigator or treating physician. If control achieved or <math>\leq</math> Grade 2, pembrolizumab may be resumed.
						

e Events that require discontinuation include, but are not limited to: encephalitis, and other clinically important irAEs (e.g. vasculitis and sclerosing cholangitis).
						

Dosing interruptions are permitted in the case of medical / surgical events or logistical reasons not related to study therapy (e.g., elective surgery, unrelated medical events, patient vacation, and/or holidays). Subjects should be placed back on study therapy within 3 weeks of the scheduled interruption, unless otherwise discussed with the Sponsor. The reason for interruption should be documented in the patient's study record.

